## **13.6 Reporting and Exclusions**

### **13.6.1 Evaluation of toxicity**

All patients will be evaluable for toxicity from the time of their first treatment with lenalidomide.

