**Table 2: Lenalidomide Dosing and Administration**

Treatment Arm	Cycle	Dose	Ancillary Medications	Schedule	Cycle Length
A Concurrent	1	2.5 mg/day	Allopurinol 300 mg/day beginning 3 days prior to lenalidomide and continuing through at least the end of Cycle 1	Days 1-28 continuous	28 days
	2+	5 mg/day	Dexamethasone may be given for up to 7 days during Cycles 1 and 2 for symptomatic tumor flare		

B Sequential	1-3	No lenalidomide	Allopurinol 300 mg/day beginning 3 days prior to lenalidomide and continuing through at least the end of Cycle 4  Dexamethasone may be given for up to 7 days during Cycles 4 and 5 for symptomatic tumor flare	Days 1-28 continuous	
	4	2.5 mg/day			
	5+	5 mg/day			

Lenalidomide dosing and administration are summarized in **Table 2**. Lenalidomide treatment will be administered at 2.5 mg/day during the first cycle of treatment (Arm A: Cycle 1; Arm B: Cycle 4) to minimize risks for tumor flare and/or tumor lysis. The dose of lenalidomide will be increased to 5 mg/day beginning as early as the second cycle of therapy (Arm A: Cycle 2; Arm B: Cycle 5) if all of the following criteria are met on Day 1:

- No clinically significant Grade 3 or greater non-hematologic toxicities attributable to lenalidomide during the preceding cycle.
- Any hematologic toxicity is resolved to  $\leq$  Grade 1.
- Maintained platelet count  $>50K$  at all times during the previous cycle.
- Maintained ANC  $>1K$  at all times during the preceding cycle.
- Any other drug-related adverse events have resolved to Grade  $\leq 1$  severity.

During the first cycle of lenalidomide exposure, and any cycle in which the dose is subsequently escalated, patients are seen on Days 1 and 8 for laboratory evaluation (CBC, chemistries), history, and physical examination to evaluate for tumor lysis and/or tumor flare, respectively. Management of tumor flare response is detailed in **5.2.1** below.

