### 5.1.2 Protein-conjugate 13-valent pneumococcal vaccine

PCV13 administration is summarized in **Table 3** below. Patients will receive 2 doses of PCV13 administered 8 weeks apart. In Arm A (Concurrent), vaccine will be administered on Day 1 of cycles 3 and 5. In Arm B (Sequential), patients will be vaccinated on Day 1 of cycles 1 and 3. Each 0.5 mL dose of vaccine will be given intramuscularly in the deltoid muscle of the upper arm. PCV13 should not be administered intravenously, intradermally, or subcutaneously.

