### Schedule of Study Assessments: Arm B (Sequential)

Procedure	Screening	Cycle 1	Cycle 2	Cycle 3	Cycle 4 & 5				Cycle 6	Cycle 7+	End of Therapy o	Follow-Up p
					W1	W2	W3	W4				
Clinical Assessment												
Informed Consent	X											
Physical Examination a	X	X	X	X	X	X	X	X	X	X	X	
ECOG Performance Status b	X	X	X	X	X	X	X	X	X	X	X	
Concomitant medications	X	X	X	X	X	X	X	X	X	X	X	
Interval infection history c		X	X	X	X	X	X	X	X	X	X	
Record adverse events		X	X	X	X	X	X	X	X	X	X	
Perform Drug Accountability d	X				X	X	X	X	X	X	X	
Education and Counseling e					X				X	X	X	
Response assessment n					C5					X n	X	X
Laboaratory Studies and Procedures												
ECG	X											
Complete blood count m	X	X	X	X	X	X	X	X	X	X	X	X
Serum chemistries f	X	X	X	X	X	X	X	X	X	X	X	
Urinalysis	X											
Quantitative immunoglobulins	X	X		X	X					Every 6 mo	X g	X
Direct and indirect antiglobulin test	X											
TSH	X										X	
Pregnancy testing g	X				X g	X	X	X	X	X	X	
Bone marrow biopsy h	Optional										X	
Risk stratification studies i	X											
CT scans r	X										X	
Anti-pneumococcal antibody titers		X		X	X							
Treatment												
Allopurinol l					X	X	X	X				
Thromboprophylaxis k					X	X	X	X	X	X		
Dispense Lenalidomide l					X	X	X	X	X	X		
Lenalidomide					X	X	X	X	X	X		
PCV13 administration		X		X								
Correlative Studies												
Pharmacokinetic Studies s					C5 D1,2							
Pharmacodynamic Studies t	X	X			C4 D1,3 C5 D1	C4 D8			X			

- a. Physical examination should include vitals signs, weight, general physical examination (including neurologic examination), measurement of liver and spleen span in centimeters below the costal margin in the anterior axillary line, and bi-dimensional measurement of cervical, supraclavicular, axillary, and inguinal nodes.
- b. See [Appendix A](#).
- c. See [6.3.10](#) for required information to be documented for each episode of infection.
- d. Patient medication diary is reviewed to assess patient compliance on the first day of each cycle in which lenalidomide is administered.

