### 13.3 Study Design

In this trial, patients will be randomized in a 1:1 allocation to receive lenalidomide with PCV13 up front concurrently (Arm A) vs. PCV13 up front and then subsequent administration of lenalidomide (Arm B). In this study we will compare the proportion of patients in each arm who achieve a significant antibody response as defined above. While it is not typical to employ a direct comparison of primary endpoints in the phase II setting, we believe that a randomized phase II design will better control for cohort and sampling variability necessary to assess the primary endpoint. In addition, in a secondary manner, we will also evaluate the clinical efficacy of treatment with lenalidomide in these patients vaccinated with PCV13, where clinical efficacy will be primarily determined through the proportion of patients who achieve a CR within two years (see Analysis Plan for more details).

Randomization will be stratified on exposure to pneumococcal vaccination in the previous 5 years. Those patients who have previously received a polysaccharide pneumococcal vaccine will not be excluded. If a patient drops out of the study prior to administration of a 2nd (booster) pneumococcal vaccination, they will not be considered evaluable for the primary endpoint and will be replaced on the study. However, the patient will be included in analyses of efficacy and tolerability as appropriate.

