#### **13.4 Sample Size/Accrual Rate**

We expect that at most 10% will potentially drop out prior to administration of the 2nd vaccination, which translates to a total maximum sample size of  $22+2=24$  in each arm for a total of 48 patients. With an anticipated accrual rate of about 3 patients per month, we expect that this trial will be fully accrued in at most 16 months.

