In each arm, we will evaluate the overall and complete response rates after two years, the proportion of patients in each arm who are progression-free at 2 years, and safety and tolerability of each regimen. Adverse events will be summarized by and across treatment arms, where we will summarize the type, severity, and perceived attribution to study treatment according to NCI's CTCAE (version 5). The rates of severe (grade 3+) toxicity (at least possibly related to treatment) and non-hematologic toxicity will be summarized; assuming the incidence of severe toxicity is binomially distributed, 95% confidence intervals will be calculated. The maximum grade for each type of toxicity will be recorded for each patient, and frequency tables will be reviewed to determine the toxicity patterns. In addition, we will assess time to treatment failure, defined as the time from study entry to discontinuation of treatment; we will also summarize reasons patients discontinue study treatment.

Descriptive statistics (i.e. means, standard deviations, 95% confidence intervals for continuous variables and frequencies for discrete data) will be computed for all correlative laboratory parameters. Given the small sample size in this phase II trial, a total of 44 patients may limit our ability to perform inferential tests. Still, we will graphically evaluate these PK and PD markers within and across arms to assess potential patterns and relationships. Where model assumptions are met, we will also utilize repeated measures models (linear or nonlinear mixed models, generalized estimating equation models) to explore relationships with the various markers and clinical outcomes of interest.

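### Toxicity evaluability starts at first lenalidomide (13.6.1), so the 13.5 toxicity rates and maximum-grade tables count acute PCV13 reactions in Arm A but not in Arm B

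*Combined protocol and SAP*

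**What the plan says.** Section 13.6.1 sets one rule for both arms: "All patients will be evaluable for toxicity from the time of their first treatment with lenalidomide".

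The arms receive the two agents in opposite order. Table 2 starts lenalidomide in Cycle 1 in Arm A and in Cycle 4 in Arm B. Section 5.1.2 gives the vaccine schedule: "In Arm A (Concurrent), vaccine will be administered on Day 1 of cycles 3 and 5", and "In Arm B (Sequential), patients will be vaccinated on Day 1 of cycles 1 and 3".

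Section 13.5 plans to evaluate the safety and tolerability of each regimen. It states that "Adverse events will be summarized by and across treatment arms". It then plans rates of Grade 3+ toxicity at least possibly related to treatment and of non-hematologic toxicity, with 95% confidence intervals, and tables of each patient's maximum grade for each toxicity type.

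Section 13.3 says of a patient who drops out before the second vaccination: "However, the patient will be included in analyses of efficacy and tolerability as appropriate". Section 13.4 sizes that group: "We expect that at most 10% will potentially drop out prior to administration of the" second vaccination.

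The Arm B calendar in Section 10 marks the row "Record adverse events" from Cycle 1, three cycles before that arm receives lenalidomide.

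**The concern.** PCV13 is part of both regimens, and the protocol lists its reactions in 7.1.1 and 8.2.6, from local erythema and induration to anaphylaxis. A window that opens at first lenalidomide opens before vaccination in Arm A and after it in Arm B. An identical acute vaccine reaction is then counted against concurrent treatment and not against sequential treatment. The schedule fixes this direction; it does not average out.

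Severe events are not the only ones affected. The maximum-grade tables take any grade, so local reactions would also be tabulated for one arm and not the other. The pooled figures are incomplete as well, because they leave out Arm B's whole vaccination period.

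The denominators differ too. An Arm B patient who stops after one or two vaccinations and before Cycle 4 has received study treatment but never enters the toxicity set. An Arm A patient who stops at the same time has been taking lenalidomide since Cycle 1 and does enter it.

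**Working it through.** **Inputs.** Cycle length is 28 days (Schema, 5.1.1). First lenalidomide is Cycle 1 Day 1 in Arm A and Cycle 4 Day 1 in Arm B (Table 2). PCV13 is given on Day 1 of Cycles 3 and 5 in Arm A and of Cycles 1 and 3 in Arm B (5.1.2, Table 3). The planned size is 22 + 2 = 24 per arm, 48 in total (13.4). The plan states no toxicity figure to reproduce.

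**Timing.** Counting from Cycle 1 Day 1 as day 0, Day 1 of cycle k falls on day 28 × (k − 1).

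| | First lenalidomide | PCV13 doses | PCV13 relative to first lenalidomide |
|---|---|---|---|
| Arm A | day 0 | days 56, 112 | +56, +112 |
| Arm B | day 84 | days 0, 56 | −84, −28 |

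The gap between doses is 112 − 56 = 56 days in Arm A and 56 − 0 = 56 days in Arm B, which reproduces the 8 weeks of 5.1.2. Both Arm A doses lie inside the 13.6.1 window and neither Arm B dose does. For the 28-day period starting with each dose, 56 of 56 days are inside the window in Arm A and 0 of 56 in Arm B.

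**Effect of one event.** Take one patient whose only related Grade 3+ event is an acute PCV13 reaction.

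- In Arm A the rate rises by 1/24 = 4.2 to 1/22 = 4.5 percentage points.
- Pooled, the same Arm A event adds 1/48 = 2.1 to 1/44 = 2.3 points.
- In Arm B the event adds nothing to either rate.

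With one such reaction in each arm and the maximum planned dropout, Arm A would report 1/24 = 4.2% (exact 95% CI 0.1 to 21.1%) and Arm B 0/22 = 0% (0 to 15.4%).

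**Denominators.** If 2 patients per arm leave before the booster, all 24 Arm A patients have had lenalidomide and remain evaluable. Arm B keeps 24 − 2 = 22, a loss of 2/24 = 8.3%. Any Arm B patient who leaves between the booster (Cycle 3 Day 1) and Cycle 4 Day 1 would be lost in addition.

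**Illustration with assumed rates.** The documents give no PCV13 reaction frequency. Let v be the chance per patient of a countable vaccine reaction and l the chance of a countable lenalidomide toxicity, independent and equal in both arms. Arm A counts 1 − (1 − v)(1 − l) and Arm B counts l, so the artificial gap is v(1 − l).

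| v (assumed) | Gap, l = 20% | Gap, l = 40% |
|---|---|---|
| 2% | 1.6 points | 1.2 points |
| 5% | 4.0 points | 3.0 points |
| 10% | 8.0 points | 6.0 points |

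These show how the gap scales with v. They do not estimate it.

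**The case against.** The best defence is that the window matches the only stated safety objective. Objective 1.2.5 concerns long-term lenalidomide exposure, no objective concerns vaccine safety, and PCV13 is commercially available. That stands for lenalidomide toxicity, and the window should be kept for it. It does not cover the regimen-level rates by arm in 13.5, and 13.6.1 draws no distinction between the two uses.

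A second point limits the reach of the concern. A reader might infer that all by-arm safety reporting omits Arm B's vaccine reactions. The documents do not support that. 13.6.1 governs evaluability for toxicity; the general adverse event summary in 13.5 has no stated start date, and 7.4 and 12.1.1 require all adverse events to be reported. The asymmetry is secure only for the toxicity rates and the maximum-grade tables.

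A reader might also infer that 13.6.1 contradicts 13.3. That is too strong. The qualifier that ends the 13.3 sentence can be read as leaving 13.6.1 to decide who counts for toxicity. The sentence also covers only patients who leave before the second vaccination, and says nothing of Arm B patients who leave between Cycle 3 Day 1 and Cycle 4 Day 1. The two sections sit awkwardly together and give no rule for choosing the Arm B safety denominator.

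Finally, the halting rule in 5.6 and the data and safety monitoring in 7.5.1 do not use the 13.6.1 window, so safety oversight during the trial is not restricted by it.

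**Conclusion.** The point holds for the 13.5 toxicity rates (Grade 3+ at least possibly related, and non-hematologic) and the maximum-grade tables, by arm and pooled. Under 13.6.1 as written, acute PCV13 reactions enter these for Arm A and not for Arm B, and Arm B patients who leave before Cycle 4 are never evaluable. No other section corrects this.

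The consequence is descriptive. No between-arm toxicity test is planned, and the primary endpoint, alpha, power and decision rules are untouched. The effect on Grade 3+ rates is probably small. The denominator difference of 24 against 22 is the case of maximum planned pre-booster dropout with no further loss before Cycle 4; 13.4 gives that dropout as an upper limit, not a forecast.

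The conclusion assumes that patients follow the planned schedule and that 13.6.1 is applied as written. An analyst who quietly included the early Arm B events would avoid the asymmetry, but would be departing from the stated rule.

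**What to change.** Replace 13.6.1 with: *For regimen-level toxicity by and across arms, all patients are evaluable from the first dose of either study agent (PCV13 or lenalidomide). For lenalidomide toxicity (objective 1.2.5), patients are evaluable from their first dose of lenalidomide.* Label the window on every safety table produced under 13.5.

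Both arms then start at Cycle 1 Day 1, all scheduled PCV13 doses fall inside the regimen-level window, and up to 24 of 24 Arm B patients are evaluable.

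Optionally, list for both arms the adverse events with onset in the 28 days from each PCV13 dose. The 28 days are a choice; they match the gap between the Arm B booster and its first lenalidomide dose. In Arm A that list will also contain lenalidomide events. If 13.3 is edited, refer tolerability to 13.6.1 and efficacy to 13.6.2, since response is governed by the latter.

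The cost is two sentences, table labels and a rerun of the safety tables on events already recorded from Cycle 1. No new data or visits are needed. The drawback is that Arm B's regimen-level window includes 3 × 28 = 84 days (12 weeks) without lenalidomide, so the two windows must be labelled and kept apart.

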### **13.6.2 Evaluation of response**

All patients included in the study must be assessed for response to treatment, even if there are major protocol treatment deviations or if they are ineligible. Each patient will be assigned one of the following categories: 1) complete response, 2) partial response, 3) stable disease, 4) progressive disease, 5) early death from malignant disease, 6) early death from toxicity, 7) early death because of other cause, or 9) unknown (not assessable, insufficient data). [Note: By arbitrary convention, category 9 usually designates the “unknown” status of any type of data in a clinical database.]

All of the patients who met the eligibility criteria (with the possible exception of those who received no study medication) should be included in the main analysis of the response rate. Patients in response categories 4-9 should be considered to have a treatment failure (disease progression). Thus, an incorrect treatment schedule or drug administration does not result in exclusion from the analysis of the response rate. Precise definitions for categories 4-9 will be protocol specific.

**APPENDIX A                    PERFORMANCE STATUS CRITERIA**

ECOG Performance Status Scale		Karnofsky Performance Scale	
Grade	Descriptions	Percent	Description
0	Normal activity. Fully active, able to carry on all pre-disease performance without restriction.	100	Normal, no complaints, no evidence of disease.
		90	Able to carry on normal activity; minor signs or symptoms of disease.
1	Symptoms, but ambulatory. Restricted in physically strenuous activity, but ambulatory and able to carry out work of a light or sedentary nature (e.g., light housework, office work).	80	Normal activity with effort; some signs or symptoms of disease.
		70	Cares for self, unable to carry on normal activity or to do active work.
2	In bed <50% of the time. Ambulatory and capable of all self-care, but unable to carry out any work activities. Up and about more than 50% of waking hours.	60	Requires occasional assistance, but is able to care for most of his/her needs.
		50	Requires considerable assistance and frequent medical care.
3	In bed >50% of the time. Capable of only limited self-care, confined to bed or chair more than 50% of waking hours.	40	Disabled, requires special care and assistance.
		30	Severely disabled, hospitalization indicated. Death not imminent.
4	100% bedridden. Completely disabled. Cannot carry on any self-care. Totally confined to bed or chair.	20	Very sick, hospitalization indicated. Death not imminent.
		10	Moribund, fatal processes progressing rapidly.
5	Dead.	0	Dead.

**APPENDIX B MEDICATION CALENDAR**

**SUBJECT DIARY**

Site #	8834	PI Name:	[name]	Subject #:	
--------	------	----------	------------------	------------	--

**Instructions:** The study drug is stored at room temperature. Please do not freeze or refrigerate the study drug. The study drug must be taken by mouth once a day with 8 ounces (approximately 240 mL) of water. The capsules should be swallowed intact. Do not open capsules or dissolve them in water.

Each dose should be taken at approximately the same time each day with or without food. If a dose is missed, it can be taken up to 6 hours after the scheduled time with a return to the normal schedule the following day. If it has been more than 6 hours, the dose should be skipped and you must take the next dose at the scheduled time the next day. The missed dose will not be made up and all the capsules from the missed dose must be returned to the clinic or hospital at the next visit.

Please complete the form below EVERY DAY to keep track of your doses. The purpose of this form is to help you remember to take the study drug once a day. For each day, complete the **date and time** (including circling “am” or “pm”) for when you took the study drug, and the **number of capsules** you took. If you experienced any **symptoms** that you feel might have been related to the study drug, write those down as well. Always take this form with you when you attend your visits with the clinic or hospital.

---

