**Table 1: Treatment Overview**

Arm A: Concurrent							
Month 1	Month 2	Month 3	Month 4	Month 5	Month 6	Month 7	Month 8+
L	L	L	L	L	L	L	L

  

Arm B: Sequential							
Month 1	Month 2	Month 3	Month 4	Month 5	Month 6	Month 7	Month 8+
V		V	L	L	L	L	L

**V** = PCV13 pneumococcal vaccine administration; **L** = lenalidomide

All patients will be instructed on how to use a medication diary documenting each dose of medication ([Appendix B](#)). At monthly visits the patient will bring the medication calendar to the clinic. All bottles of study medication should be brought to each clinic visit for comparison with the medication calendar. The medication calendar for the previous month will be reviewed, and a new medication calendar will be given to the patient with each new lenalidomide supply.

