### 6.3 Criteria for Dose Reductions

Dose modifications of lenalidomide may be made at any time during treatment if lenalidomide is held for toxicity or at the start of a new cycle if the previous dose was not well-tolerated. Lenalidomide dose levels are displayed in [Table 4](#). No dose reductions below dose level -1 (2.5 mg every other day) will be permitted. Specific criteria for holding and/or modifying the dose of lenalidomide are further detailed in this section.

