**Table 4. Lenalidomide Dose Levels**

Dose Level	Lenalidomide Dose
1	5 mg daily
0	2.5 mg daily
-1	2.5 mg every other day

If a toxicity requiring dose reduction is experienced, appropriate measures will be taken as described below (6.3.1), and when therapy with the study drug resumes it will be considered the next day of the patient's current cycle. For example, if drug is held prior to the daily dose on day 8 for a toxicity, and the toxicity resolves to allow lenalidomide resumption after 7 days, it would then be considered day 8 of the current cycle.

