### 6.3.1 Hematologic Toxicity

- In the instance of Grade  $\geq 3$  lenalidomide-related hematologic toxicity on day 1 of a cycle, delay lenalidomide therapy and monitor CBC at least weekly. If toxicity resolves to Grade  $\leq 1$  within 2 weeks, then resume lenalidomide at the next lower dose level.
- If Grade  $\geq 3$  lenalidomide-related hematologic toxicity occurs during a cycle, delay lenalidomide therapy and monitor CBC at least weekly. If toxicity resolves to Grade  $\leq 1$  within 2 weeks, then resume lenalidomide at the next lower dose level.
- If treatment is delayed for more than 2 weeks, discontinue protocol therapy.
- WBC colony stimulating factors may not be used to avoid dose reductions but can be used in the treatment of febrile neutropenia as outlined in 6.3.2 below.
- Because of the potential to increase the risk for venous thromboembolic disease, the use of erythropoietic stimulating agents (ESAs) will not be permitted.
- Because a decrease in absolute lymphocyte count (and thus WBC count) is an expected therapeutic outcome of treatment with Lenalidomide, no dose modification is required for the AEs of White Blood Cell Decreased or Lymphocyte Count Decreased.

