### **Patient Care Implications and Counseling: Risks Associated with Pregnancy**

Lenalidomide is structurally related to thalidomide. Thalidomide is a known human teratogenic active substance that causes severe life-threatening birth defects. An embryofetal development study in animals indicates that lenalidomide produced malformations in the offspring of female monkeys who received the drug during pregnancy. The teratogenic effect of lenalidomide in humans cannot be ruled out. Therefore, a risk minimization plan to prevent pregnancy must be observed.

Definition of female of childbearing potential (FCBP)

This protocol defines a female of childbearing potential as a sexually mature woman who: 1) has not undergone a hysterectomy or bilateral oophorectomy or 2) has not been naturally postmenopausal (amenorrhea following cancer therapy does not rule out childbearing potential) for at least 24 consecutive months (i.e., has had menses at any time in the preceding 24 consecutive months).

Before starting study drug:

Female Subjects:

- FCBP must have two negative pregnancy tests (minimum sensitivity of 25 mIU/mL) prior to starting study drug. The first pregnancy test must be performed within 10-14 days prior to the start of study drug and the second pregnancy test must be performed within 24 hours prior to the start of study drug. The subject may not receive study drug until the Investigator has verified that the results of these pregnancy tests are negative.

Male Subjects:

- Must agree to use a latex condom during sexual contact with females of childbearing potential while participating in the study and for at least 28 days following discontinuation from the study even if he has undergone a successful vasectomy.

All Subjects:

- Only enough lenalidomide for one cycle of therapy may be dispensed with each cycle of therapy.
- If pregnancy or a positive pregnancy test does occur in a study subject or the partner of a male study subject during study participation, lenalidomide must be immediately discontinued.

Counseling

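### The patient diary orders daily lenalidomide even for patients reduced to every-other-day dosing, and its missed-dose rule disagrees with Section 5.1.1

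*Combined protocol and SAP*

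**What the plan says.** **Dosing frequency.** Section 6.3 sets the floor for reductions: "No dose reductions below dose level -1 (2.5 mg every other day) will be permitted". Table 4 gives three levels: 5 mg daily (level 1), 2.5 mg daily (level 0) and 2.5 mg every other day (level -1). After a qualifying toxicity has resolved in time, Section 6.3.1 tells the site to "resume lenalidomide at the next lower dose level", and Section 6.3.12 does the same for other non-hematologic toxicity. A patient at level 0 therefore goes to level -1.

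The diary is universal. Section 5.1, below Table 1, says: "All patients will be instructed on how to use a medication diary documenting each dose of medication". Its instructions in Appendix B read "The study drug must be taken by mouth once a day with 8 ounces (approximately 240 mL) of water" and, further down, "The purpose of this form is to help you remember to take the study drug once a day". The form has 28 daily rows for date, time, capsule count and symptoms. It has no field for dose level or schedule.

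**Missed doses.** Appendix B says of a missed dose that "it can be taken up to 6 hours after the scheduled time with a return to the normal schedule the following day". After 6 hours the dose is skipped and the next one is taken at the usual time the next day. Section 5.1.1 works by the day instead: the patient takes the dose when it is remembered that day, skips it if it is not remembered until the next day, and never takes two doses on one day.

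**The concern.** Level -1 is reached only by reduction for toxicity, and frequency is the only thing that separates it from level 0. The diary contradicts that one feature, so a patient who follows the printed instruction undoes the reduction. Level -1 is also the lowest step allowed, so toxicity that recurs at an unintended daily rate leaves no lower level to move to.

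The missed-dose conflict does not depend on a dose reduction. Any patient on lenalidomide has two incompatible rules, and which is the stricter depends on the hour at which the dose is due. What is at stake is correct dosing and patient safety, not the analysis.

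**Working it through.** The plan gives no figure of its own here, so the check compares the texts and works out the consequences.

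**Inputs.** Cycle of 28 days (Section 5.1.1). Level 0 is 2.5 mg daily and level -1 is 2.5 mg every other day (Table 4). The day-8 restart comes from the example under Table 4: "if drug is held prior to the daily dose on day 8 for a toxicity". Supply is limited by Section 8.1: "Only enough lenalidomide for one cycle of therapy may be dispensed with each cycle of therapy". Assumptions: a patient reduced mid-cycle keeps the level 0 capsules at home, and a patient who starts a cycle at level -1 is given 14 capsules.

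**1. Mid-cycle reduction from level 0 to level -1.** Excess = (daily doses − alternate-day doses from restart to day 28) × 2.5 mg.

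For a day-8 restart, 28 − 7 = 21 capsules remain.
- Diary followed: 21 × 2.5 = 52.5 mg.
- Table 4 followed (days 8, 10, …, 28): 11 × 2.5 = 27.5 mg.
- Excess: 25 mg.

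| Restart day | Daily doses | Alternate-day doses | Excess to day 28 |
|---|---|---|---|
| 2 | 27 | 14 | 32.5 mg |
| 8 | 21 | 11 | 25 mg |
| 15 | 14 | 7 | 17.5 mg |
| 22 | 7 | 4 | 7.5 mg |

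These are upper bounds, with no correction before day 28. If the error is found one week after a day-8 restart, the excess is (7 − 4) × 2.5 = 7.5 mg just before that day's dose, or (8 − 4) × 2.5 = 10 mg just after it.

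**2. New cycle started at level -1 with 14 capsules.** Taken daily, the supply is gone by day 14: 14 × 2.5 = 35 mg, against 7 × 2.5 = 17.5 mg assigned by then. The rate doubles for 14 days, but the 28-day total is 35 mg either way.

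**3. Missed-dose window.** For a dose due at clock hour T, Section 5.1.1 allows 24 − T hours (to midnight) and the diary allows 6. They are equal when 24 − T = 6, that is T = 18 (6 pm).

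| Dose due | Section 5.1.1 | Diary | Conflict |
|---|---|---|---|
| 8 am | 16 h | 6 h | 2 pm to midnight: 5.1.1 says take, diary says skip |
| 6 pm | 6 h | 6 h | none |
| 8 pm | 4 h | 6 h | midnight to 2 am: diary permits, 5.1.1 says skip |

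In the 8 pm case, suppose the diary's return to the normal schedule is counted from the day the dose was due. A dose taken at 2 am is then followed by one at 8 pm on the same date, 18 hours later, and Section 5.1.1 forbids two doses in a day.

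**The case against.** The strongest reply is that Appendix B is a generic form for the usual regimen. Levels 1 and 0 are both daily, the treating team assigns the level, and a patient can leave off days blank or enter zero capsules. On that view the diary omits an exception rather than contradicting the protocol.

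There are also safeguards:
- Section 5.1 has patients bring all bottles to each visit for comparison with the calendar, and the previous month's calendar is reviewed.
- Section 5.1.1 requires a compliance review before each new supply. Counseling precedes dispensing, and the Appendix E sheet (text not available here) is read each time and might state the schedule correctly.
- Holds require at least weekly monitoring, so staff direct the restart. Weekly blood counts follow a hematologic reduction (Section 10, footnote m), and weekly chemistry follows a tumor lysis restart (Section 6.3.9).
- The calendars mark weekly columns in the first two lenalidomide cycles, although Section 5.1.1 describes visits on days 1 and 8 only.

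On missed doses, any one patient meets the conflict in one direction only. Before 6 pm the diary is merely more cautious. After 6 pm it permits rather than requires the late dose, and the two-dose breach depends on one reading of the wording.

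Most of this stands as a limit on likelihood and size. It does not remove the fault. The diary's instruction is mandatory in form and unqualified, and the bottle and compliance reviews find an error at the next visit without preventing it within the cycle. For other non-hematologic reductions from the third lenalidomide cycle on, the calendars show one visit column per cycle. No dosing hour is fixed and the diary offers am and pm, so both directions of the missed-dose conflict can occur in the trial.

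**Conclusion.** The concern holds: Appendix B is wrong as written on both counts, and the severity is minor. For a mid-cycle reduction to level -1, the excess is at most 25 mg from a day-8 restart, ranging from 7.5 mg (day 22) to 32.5 mg (day 2). That rests on capsules kept at home, a patient who follows the form rather than the clinician's restart instruction, and no correction before day 28. For a cycle begun at level -1 with 14 capsules, the rate doubles for 14 days with no excess over the cycle. The missed-dose rules agree only for a dose due at 6 pm; two doses on one date is a possible result that depends on the reading.

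The number of patients at level -1 is not given, and Section 9 says few patients remain on treatment. No endpoint, power, sample size or compliance rule is affected.

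**What to change.** In Appendix B:
- replace the once-daily wording, in both places, with an instruction to take the drug on the schedule prescribed for the current dose level;
- add a field for dose level and schedule;
- for level -1, issue an every-other-day version or mark the dosing days, including when the reduction is made mid-cycle and capsules are already at home;
- after a skipped dose, refer to the next scheduled dosing day instead of the next day.

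Use one missed-dose rule in both Section 5.1.1 and Appendix B that rules out two doses on the same day, for example a fixed window that also ends at midnight. The clinical team should set its length.

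The cost is one revised diary page and one aligned sentence in Section 5.1.1. Design, sample size and analysis do not change.
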